The Neural Effects of Balance Versus Aerobic Training in Individuals With Degenerative Cerebellar Diseases

NCT05002218

February 21, 2025

BACKGROUND

Abstract

Exercise is the main treatment for degenerative cerebellar diseases, a group of disorders that affect cerebellar neurons causing an array of symptoms including an inability to coordinate balance, gait, and extremity movements. Studies researching the effect of balance training on degenerative cerebellar disease have found functional improvements in patient's walking.

The role of aerobic exercise in the treatment of degenerative cerebellar disease is relatively unknown. Research on rats with symptoms similar to cerebellar ataxia indicates that moderate aerobic exercise increases the rat's lifespan compared to rats that do not exercise. Studies of other neurological diseases, such as Parkinson's disease, illustrate that aerobic exercise enhances motor learning in the brain. Only one study to date has assessed the effectiveness of aerobic exercise on cerebellar ataxia in humans. Patients were given a 4-week cycling regime consisting of 15 minutes per day, 3 days per week. Results indicated that patients in the cycling group had improved ICARS scores (a scale used to monitor ataxia), but not gait speed or standing capacity compared to a control group. Other measures of balance were not tested in this study. The main objective of this project will be to compare the benefits of aerobic versus balance training in DCD. We hypothesize that both aerobic and balance training will improve function in ataxic subjects, but that the mechanisms in which these improvements occur differ.

Study Purpose and Rationale

Heredity spinocerebellar diseases are a group of disorders in which cerebellar degradation manifests in ataxia, a neurological sign causing impaired coordination and balance.¹ The diseases are devastatingly debilitating with many individuals requiring wheelchairs for locomotion after only 10 to 15 years from initial diagnoses. With no disease modifying medications currently available, balance training is recommended to improve motor skills and maintain function. Yet, recent emerging evidence from our research group shows that aerobic training is a promising treatment option. The goal of this study is to compare the impact of balance versus aerobic training on the brains of individuals with hereditary spinocerebellar diseases. Prior research has used clinical measures, such as the Scale for the Assessment and Rating of Ataxia (SARA), to determine the benefits of training. Although validated for this purpose, these scales

cannot differentiate between functional compensation of deficits versus slowing of cerebellar degradation. Thus, it is important to examine the neurological impact of different training methods to distinguish whether one training method is better able to slow disease progression than the other. Moreover, we speculate that aerobic and balance training impact the brain via different mechanisms. Two hypotheses exist regarding the neural effects of training; the degenerating cerebellum undergoes neuroplastic changes to adapt its functioning, or alternatively, other brain areas undergo neuroplastic changes to compensate for deficits. We hypothesize that balance training causes improvements for people with cerebellar degeneration by impacting brain structures outside the cerebellum whereas aerobic training induces neuroplastic changes within the cerebellum. We expect this result because:

1) A 2-week balance training program resulted in increased grey matter volume in the premotor cortex of individuals with cerebellar degeneration, but no statistically significant changes in the cerebellum.

2) Ataxic animals that regularly perform aerobic exercise have larger cerebellums with increased synapses and dendrites at death than those who are sedentary.

3) Preliminary data from our group indicates increased cerebellar volume in individuals with spinocerebellar disease who participate in a 6-month home aerobic program, but decreased volume for those who perform balance training. Thus, if our hypothesis is true, aerobic training may have more influence on disease progression than balance training as it directly impacts the cause of deficits, the cerebellum.

Public Health Significance: There is a critical need to determine effective treatments for hereditary cerebellar diseases. Research has shown balance and aerobic training improves symptoms for individuals with these disorders, but the mechanisms of improvement are unknown. This proposal will begin to examine the impact of both training methods on the brain. By understanding how each training method impacts cerebellar volume, microstructure, and functional connectivity, future research can more precisely target training regimens with the goal of slowing the disease progression of individuals with these devastating diseases.

Research Aims & Abstracts

AIM 1) To determine the effect of training on cerebellar volume. Individuals with hereditary spinocerebellar ataxias will be randomized to either a 6-month home aerobic or balance

training program. Structural MRI scans will be taken before and after the training programs to determine the impact of training on cerebellar volume. We hypothesize that aerobic training will slow cerebellar volume loss when compared to balance training.

AIM 2) To evaluate the long-term training effects on clinical measures of ataxia and correlate changes with cerebellar volume. SARA scores will be determined before and after each training program. They will also be taken at 3- and 6-months post-training along with structural MRI scans. Consistent with our prior research, we hypothesize that improvements in SARA scores will revert back to baseline if training is halted. We further hypothesize that changes in SARA scores will correlate with cerebellar volume changes in the aerobic group, but not with changes in the balance group.

Exploratory Aim 3) To examine the effects of exercise on cerebellar microstructure and functional connectivity to the cerebellum. Diffusion weighted imaging and resting state fMRI scans will be taken before and after individuals with spinocerebellar disease participate in a 6-month home aerobic or balance training program. We will then use the cerebellum as our region of interest to analyze how training impacts cerebellar microstructure and functional cerebellar connections. Although the impact of training on the cerebellum has been investigated in healthy individuals, it is unclear how training will impact the degenerating cerebellum in our subject population. Thus, we will use this preliminary data to determine which cerebellar regions and functional networks are most impacted by training to form targeted hypotheses for future research projects.

STUDY DESIGN

This is a single-blinded randomized control trial. After initial testing, participants will be randomly assigned to either home balance or aerobic training for 6 months. After training, individuals will undergo post-training testing. At the post-training testing, individuals will be encouraged to continue training, but not required to as part of the study. Follow-up testing will then be conducted at 3- and 6-month post-training to evaluate the longevity of training effects.

The rationale for this study design is as follows:

1) Randomization between balance and aerobic training groups will balance known and unknown confounding factors that may influence changes in cerebellar volume. Individuals

conducting assessments will be blinded to group, but participants cannot be blinded given the nature of the intervention.

2) Although the use of an active control (balance training) as opposed to a placebo control may make it more difficult to detect differences between groups, our preliminary data made us comfortable that we would be able to detect differences. This design also allows us to examine the neural mechanisms underlying balance training effects on individuals with spinocerebellar disease in addition to aerobic training.

3) 6-months of training was used for this study because prior work in our laboratory on healthy individuals showed that 6-months of training was long enough to detect statistically significant changes in brain volume.

4) Follow-up testing was selected to start at 3 months post-training because our prior research showed that clinical effects were still seen at this timepoint.

Study procedures

Video Recording: We will record SARA measures in order to blind researcher to intervention. The study team will use a small hand-held recorder to video the SARA test. The video will have full facial features, but the participant's name will not be attached to the recording. Analysis of the recording will only be done by members of the research team. The recording will not be used for other purposes such as teaching or commercial purposes. The recordings will be stored in a password protected database. The recording will be destroyed upon completion of the study procedures. There is no compensation for allowing video recording. These recordings will not be used in publications. They will only be used by members of the research team for evaluation purposes.

Dynamic Gait Balance: Patients will be asked to walk 20 feet and conditions such as speed and head position will be varied as previously described. The examiner will then grade the subject's movement as detailed from Shumway-Cook & Woollacott Motor Control: Theory and Practical Applications, 1995.

Gait Speed: Participants will walk as fast as possible on a 9-m runway 3 times, and we will average the results of trials.

SARA scores: SARA is an 8-item performance based scale, yielding a total score of 0 (no ataxia) to 40 (most severe ataxia). The scores are based on patient performance of gait, stance,

sitting, speech disturbance, finger chase, nose-finger test, fast alternating hand movements and heel-shin slide.

Cardiopulmonary Exercise Testing (CPET): Maximal oxygen consumption (VO₂max) will be determined by a breath-by-breath measurement of VO₂ with a Vmax Encore Metabolic System (CareFusion Corp, San Diego, CA), while participants perform a progressive ramped exercise test using an electronic-braked lower body cycle ergometer. Prior to testing, patients will be asked about prior heart conditions, joint pain, exercise intolerance, prior exercise levels, and medications. A physician will determine if the participant is eligible to participate at this time. Testing protocol includes a 3-minute warm-up at minimal resistance, and then the initial workload and individualized ramping protocol will be determined based on patient's weight, level of function, and current exercise profile. The patient will then cycle at 60-65 revolutions per minute (RPM) until achieving one of the following VO₂max criteria: respiratory exchange ratio (RER) 1.1, increases in ventilation without concomitant increases in VO₂, and/or maximum age-predicted heart rate. The test will also be terminated if the cycling cadence drops below 40 RPM for 5 seconds, or when the participant reaches volitional exhaustion. The results of this test will be used to determine initial heart rate goals of participants assigned to aerobic training.

Cerebellar Volume and Atrophy Rate: Cranial MRI will be performed in all participants using a 3-T scanner. Brain volume measurement software, FreeSurfer, will be used to calculate cerebellar volumes using Digital Imaging and Communications in Medicine (DICOM) data from T1-weighted sagittal images. We will also measure each participant's cranial anteroposterior (AP) diameter as defined by the distance in which the skull and anterior commissure-posterior commissure line intersect. For statistical analysis, the cerebellar volume will be divided by each cranial AP diameter to correct for head size differences. The difference between cerebellum volumes over a 6-month period will be used to calculate cerebellar atrophy rates.

Diffusion Tensor Imaging: This measure will be a primary outcome of Aim 3. Diffusion data will be preprocessed for motion and corrected for geometrical distortion using ExploreDTI. For each participant, the bmatrix will be reoriented to provide a more accurate estimate of diffusion tensor orientations. Diffusion tensor estimation will be performed using a non-linear least square fitting method. FA and Mean Diffusivity (MD) maps will be generated. Whole brain tractography will be performed using all brain voxels with FA 0.2 as seed region. Streamlines will be propagated using an Euler integration tractography algorithm with a step size of 0.5 mm and with an angular

and anisotropy threshold of 45 degrees and FA 0.2 respectively. Finally, diffusion tensor maps and whole brain tractography will be exported to TrackVis version 0.5.2.2 for manual dissection and quantification of cerebellar fiber tracts.

To determine cerebellar fiber tracts, we will use TrackVis to select regions of interest in the b0 images. The anatomical structure corresponding to the desired regions of interest will be initially localized in MRI atlases of the cerebellum, subsequently identified in T1 images, and then selected in the co-registered b0 dataset. The following regions of interest will be selected: 1) fastigial nucleus, 2) interpositus nucleus, 3) superior cerebellar peduncle, 4) middle cerebellar peduncle, and 5) inferior cerebellar peduncle. In order to extract clean diffusion measurements avoiding crossing and complex white matter regions, regions of interest will be selected using a manual two region approach.

Resting State Functional MRI: This measure will be a primary outcome for Aim 3. The anatomical and functional data will be pre-processed and analyzed using Statistical Parametric Mapping (SPM12) and the CONN toolbox Version 14p. Functional data will be pre-processed using a slice scan time correction, realignment (motion correction), registration to structural images and spatial normalization to Montreal Neurological Institute (MNI) standardized space, smoothing with a Gaussian filter of 5.0 mm spatial full width at half maximum value. A conventional band-pass filter over a low-frequency window of interest (0.008–0.09) will also be applied to the resting-state time series. After these preprocessing steps, we will extract signal to noise from the white matter and cerebrospinal fluid by principal component analysis without affecting intrinsic functional connectivity. These components, white matter, cerebrospinal fluid, and motion parameters, will be included in the model and considered as covariates of no-interest.

To determine the region of interest within the cerebellum, a localizer scan will be performed after resting fMRI as described in MRI acquisition. We focused on the legs because gait abnormalities are the main deficits in individuals with spinocerebellar ataxia. The coordinates of the region of interest within the cerebellum will be selected on the basis of activation peaks obtained from the block design analysis. For each subject, we will obtain the mean BOLD signal of the region of interest by defining a mask around the seed in the standard space. To ensure that distortion was not present in localizer scans, we will verify that head motion does not exceed a threshold of 1mm and run a general linear model with predictors associated with the movement conditions to ensure there is not activation of voxels outside the brain.

Aerobic training group: Participants will be given a stationary exercise bike for home use. They will be instructed to use the exercise bike five times a week for thirty-minute sessions. The exercise intensity prescription will be based on the subject's maximum heart rate based on age. The exercise program will start at 60% of max heart rate, and then will be increased by steps of 5% intensity every 2 weeks until participants reach 30 minutes of training at 80% intensity. In addition, rate of perceived exertion (Borg scale) will be assessed at each training session. Participants will be contacted weekly by e-mail or phone to answer any questions about the exercise protocol and will be instructed to log each training session. Subjects will record duration of exercise, perceived exertion, average heart rate, maximum heart rate, and distance. Subjects will be asked to use the bike for 6 months.

Balance training group: A home balance training program will be tailored for each participant based on pre-training capabilities. Subjects will be asked to perform exercises five times a week for thirty-minute sessions. Both dynamic and static exercises will be performed in sitting and standing positions. Exercises will start with stabilizing in a challenging static position and progress to dynamic arm and leg movements in the same or modified position. Participants will be contacted weekly by e-mail or phone to answer any questions about the exercise protocol and will be required to log their exercise effort in terms of frequency and level of balance challenge. Individuals will be instructed to perform more difficult exercises if balance challenge scores are low. Participants will be asked to do balance training program for 6 months.

STATISTICAL PROCEDURES

All analysis will be conducted blind to which intervention is being evaluated. SAS (version 9.4) will be used for all statistical analyses. We will use intention to treat principles. Demographic and clinical variables will be compared using the Wilcoxon's test and chi-squared analysis for continuous and categorical variables, respectively. The association between cerebellar volume change and SARA score change will be estimated with Spearman's correlation coefficient. We will use linear mixed-effect regression analysis to test whether change in cerebellar volume differed between training groups, controlling for age and other co-variates mentioned above as fixed effect. To account for within-subject correlation due to repeated measurement, we will include a random

intercept. If the assessment effect is significant ($p < 0.05$), post hoc analysis will be performed using pairwise comparisons between assessments.

For diffusion tensor imaging, individual ANCOVAs will be determined for FA and MD in the middle of both hemispheres for the regions of interest, with age, gender, and disease type as covariates.

For resting fMRI analysis, the mean BOLD time course of the regions of interest will be used as a predictor in a multisubject general linear model to evaluate the functional connectivity of that seed with every voxel in the brain. In addition, to account for potential contributions of physiological noise, the time course of nuisance signals of white matter, cerebrospinal fluid, and six motion parameters will be included as predictors in the same general lineal model. The analysis will end with an activation map of all voxels in the brain that correlate with the seed of interest. We will minimize detection of false positives by using a cluster-corrected family wise error rate correction at $p < 0.05$. The correction procedure will use Monte Carlo simulations to calculate the probability of having a cluster of a certain size being due to chance alone. Our z-statistic images will then be projected onto the inflated template brain. The analysis will be conducted separately for pre-training and post-training scans. For further group analysis, we will use random-effects analysis to compute comparison before and after training. To investigate the strength of connectivity changes at the single-subject level, we will calculate the values for each voxel underlying the connectivity maps in individual participants. These values will represent the strength of connectivity between the seed area and individual voxels. Analyses of the distribution of the values across subjects will be done to estimate connectivity patterns.

Sample Size Calculation: 11 subjects had completed our preliminary study with structural MRI scans before and after training. The data shows a change in cerebellar volume of $-1.06\% \pm 0.53$ for the balance group, and a cerebellar volume increase of $+1.28\% \pm 1.04$ for the aerobic group. The calculated effect size was 2.34. Setting $\alpha = 0.05$ and $\beta = 0.2$ and using a conservative effect size of 1.34 and a standard deviation of 1.3 (as seen in our pilot data), we determined that we will require 16 subjects per group for this study.

Dropout and Compliance Rate: In our current study looking at 6 months of balance verse aerobic training in this population, we currently have a drop-out rate of 11.8%. Using a slightly higher drop-out rate of 20%, we will require 20 subjects per group. In addition, 85% of participants in our pilot study met training goals. Studies with similar training programs show more modest

compliance rates of around 75%.⁷²⁻⁷⁴ Using a compliance rate of 75%, we will need to recruit 24 subjects per group. Based on previous studies, we expect to recruit about 24 subjects per year and will plan on 2 years of recruitment.

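### Aim 2 predicts that SARA gains revert if training stops, but training after month 6 is optional and no record of it is described, so sustained or partly reverted SARA could not be tied to stopping or continuing

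*Combined protocol and SAP*

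**What the plan says.** All references are to the combined protocol and SAP.

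- **Research Aims & Abstracts, AIM 2.** The aim opens "To evaluate the long-term training effects on clinical measures of ataxia". SARA and structural MRI are repeated 3 and 6 months after training. The first hypothesis reads: "we hypothesize that improvements in SARA scores will revert back to baseline if training is halted". A second concerns the correlation of SARA change with volume change.
- **STUDY DESIGN.** At the post-training visit, "individuals will be encouraged to continue training, but not required to as part of the study". Follow-up testing is there "to evaluate the longevity of training effects".
- **Study procedures, Aerobic and Balance training groups.** Exercise logs and weekly contact are described inside the two programmes, each lasting 6 months. The logging sentences have no end date of their own, and nothing extends them past month 6.
- **Study procedures, Cardiopulmonary Exercise Testing.** Before this test, "patients will be asked about prior heart conditions, joint pain, exercise intolerance, prior exercise levels, and medications", and the ramp takes account of how much the patient currently exercises. Neither item is tied to the follow-up visits. The stated use is: "The results of this test will be used to determine initial heart rate goals of participants assigned to aerobic training".
- **STATISTICAL PROCEDURES.** Intention to treat applies. SARA change enters a Spearman correlation with volume change. Clinical variables are compared by Wilcoxon's test, without saying at which visit. The mixed model, and the pairwise comparisons between assessments that follow it, are described for cerebellar volume.

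**The concern.** The hypothesis is conditional on stopping, so testing it requires knowing who stopped. The design leaves stopping to the participant, and the text describes no way of finding out. It also names no analysis that carries training status after month 6.

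The ambiguous result is a plausible one. The fourth design rationale says the first follow-up was set at 3 months because earlier work still saw clinical effects then. If SARA stays improved, the trial could not separate a lasting benefit from continued training. If mean SARA only partly reverts, it could not say whether those who stopped had reverted. If training is not asked about at the visits, it can be recovered later only by longer recall.

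**Working it through.** **1. What testing the hypothesis needs, against what is described**

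| Needed | Described |
|---|---|
| Who stopped after month 6 | Continuation optional; no record described |
| SARA after month 6 | Yes, at 3 and 6 months post-training |
| An analysis of SARA across visits | None; the Wilcoxon comparison of clinical variables may cover SARA but may be baseline only |
| Training status in that analysis | None; the model's covariates beyond age are said to be given above but are not listed there |

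**2. How far a SARA mean can be interpreted without the record**

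The documents give no SARA gain and no continuation rate, so every share here is an assumption. Let c be the share continuing, k the share of the gain kept by continuers, s the share kept by stoppers, and m the mean share kept:

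m = c × k + (1 − c) × s, so s = (m − c × k) / (1 − c).

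Taking k = 1:

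| Observed m | c = 0 | c = 0.25 | c = 0.50 | c = 0.75 |
|---|---|---|---|---|
| 0.50 | s = 0.50 | s = 0.33 | s = 0 | not possible with s ≥ 0 |
| 0.75 | s = 0.75 | s = 0.67 | s = 0.50 | s = 0 |

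If 0 ≤ s ≤ k ≤ 1, a mean of 50% kept fits any s from 0 (hypothesis true) to 0.50 (hypothesis false). The range widens if stoppers fall below baseline, which is possible in a progressive disease: c = 0.75, k = 1, s = −1 gives 0.75 − 0.25 = 0.50 as well.

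At m = 0 with s ≤ k, s cannot exceed 0 whatever c is. A full mean return to baseline is therefore consistent with the hypothesis, although it still could not be tied to stopping.

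**3. What a record would deliver**

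The plan's own figure first. For a volume difference of 1.34 with SD 1.3, two-sided alpha 0.05 (sidedness assumed) and 80% power, n = 2 × (1.960 + 0.842)² × (1.3/1.34)² = 14.8, so 15 per group. The t-based solution is 15.8, so the stated 16 reproduces. Then 16/0.80 = 20, as stated. I take the planned recruitment of 24 per group as given. These figures are for volume and serve SARA only as an illustration.

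Under intention to treat, non-compliers stay in the analysis and only dropout removes people: 24 × 0.80 = 19.2, about 19 per arm. The number stopping is n = 19.2 × (1 − c), rounded. The 95% CI half-width for their mean SARA change, in SDs of that change, is t(0.975, n − 1)/√n.

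| Assumed c | Stop, of about 19 per arm | Half-width | Stop, of 16 per arm | Half-width |
|---|---|---|---|---|
| 25% | 14 | 2.160/√14 = 0.58 SD | 12 | 2.201/√12 = 0.64 SD |
| 50% | 10 | 2.262/√10 = 0.72 SD | 8 | 2.365/√8 = 0.84 SD |
| 75% | 5 | 2.776/√5 = 1.24 SD | 4 | 3.182/√4 = 1.59 SD |

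No further loss after month 6 is assumed.

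**The case against.** The strongest defence is that the two sections do not contradict each other. The hypothesis is a conditional expectation drawn from earlier work, while the stated purpose of follow-up is the longevity of effects. Under intention to treat, the course by assigned arm with optional continuation is a coherent target. This stands: follow-up can answer that question. It does not answer the narrower one that Aim 2 also states, because a description by arm does not identify who stopped.

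A second defence is that the case rests on silence in a short public text. Logging has no stated end date, current exercise is considered before exercise testing, and repeat exercise testing at follow-up is neither stated nor excluded. This also stands in part, so the claim is only that no record is described. Even if logs continued, no described analysis would use them.

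A third defence is that a comparison of stoppers with continuers would be small and self-selected. That is true. It limits what the fix can deliver but does not make the present wording testable.

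A reader might infer that the Spearman correlation is the only analysis that could touch SARA. The text does not support this, because the Wilcoxon comparison of clinical variables is not expressly limited to baseline. It would not carry training status either way.

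**Conclusion.** The point holds as a limited one. As described, the trial cannot tie sustained or partly reverted SARA to stopping or continuing, so one Aim 2 sub-hypothesis cannot be tested as worded if either result occurs. The size of the ambiguity depends on assumed shares: a mean of 50% kept leaves the stoppers' share anywhere from 0% to 50% if 0 ≤ s ≤ k ≤ 1, and wider otherwise. That the mean alone cannot separate these cases does not depend on the particular values chosen.

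A reader might go further and infer that follow-up is uninterpretable or that Aim 2 as a whole fails. The documents do not support that. The course by assigned arm remains describable, full mean reversion remains consistent with the hypothesis, and Aim 1, the sample size and the SARA-volume correlation are unaffected. The change is worth making because it is cheap, not because the trial's main comparison is at risk.

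**What to change.** AIM 2 and STUDY DESIGN should be reconciled. This can be done without altering what participants are told about continuing, on which this review takes no position.

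1. At the existing 3- and 6-month post-training visits, record whether, how often and for how long each participant has trained since the last visit. Use a self-completed form, or existing staff other than the blinded assessors. The plan says individuals "conducting assessments will be blinded to group" and, of the videos, "We will record SARA measures in order to blind researcher to intervention"; asking about training must not undo that.
2. State the follow-up hypothesis as the course of SARA and volume by assigned arm after a 6-month programme with optional continuation. Name the analysis of SARA across visits, for example the mixed model already given for volume.
3. Report continuation by arm. Describe SARA change by recorded training status, with confidence intervals, as observational. Use 'halted' only for participants with recorded cessation.

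The cost is a few questions at two visits and a reworded hypothesis. The downsides are slight participant burden, recall error over about 3 months, and an imprecise, self-selected comparison with the half-widths shown above. That comparison would not be a causal test of halting, and it would not separate disease progression from loss of training effect. If some follow-up visits have already taken place, items 2 and 3 remain available, with training information resting on longer recall.

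### With two trained arms and a degenerative disease, randomization identifies only the aerobic-minus-balance difference; the plan's per-arm wording and before-after analyses go further.

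*Combined protocol and SAP*

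**What the plan says.** Under STUDY DESIGN, "participants will be randomly assigned to either home balance or aerobic training for 6 months". Item 2 of the design rationale concedes a drawback, "Although the use of an active control (balance training) as opposed to a placebo control may make it more difficult to detect differences between groups", and then names a benefit: "This design also allows us to examine the neural mechanisms underlying balance training effects on individuals with spinocerebellar disease in addition to aerobic training". The Public Health Significance paragraph sets out what should follow from the study: "By understanding how each training method impacts cerebellar volume, microstructure, and functional connectivity", future work can target training regimens better.

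The main hypothesis is comparative. Aim 1 states: "We hypothesize that aerobic training will slow cerebellar volume loss when compared to balance training". STATISTICAL PROCEDURES matches it: "We will use linear mixed-effect regression analysis to test whether change in cerebellar volume differed between training groups".

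Other planned analyses are contrasts over time:
- The resting-fMRI group analysis compares scans before training with scans after it. No contrast between arms is named.
- For the mixed model, a significant assessment effect leads to post hoc pairwise comparisons between assessments.
- The diffusion-tensor ANCOVAs list age, gender and disease type as covariates but do not name the factor under test.

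The documents describe no untrained or delayed-start arm, no run-in period and no rate of cerebellar volume change without training.

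**The concern.** The population has progressive cerebellar degeneration, and Aim 1 itself presupposes volume loss over time. Change in either arm over 6 months is then the sum of what the training did and what the disease did. Randomization makes the disease part equal in expectation between arms, so it cancels in the difference. It does not cancel within an arm.

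The wording quoted above implies that neural change can be attributed to balance training, and to aerobic training, separately. If the before-after analyses are run as planned, a decline in the balance arm or a shift in connectivity could be reported as a mechanism of training when it is partly or wholly disease course. Aim 3 is meant to identify the regions and networks that training affects most, as a basis for later hypotheses, so a misattribution would carry forward.

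**Working it through.** **Inputs.** All are from Sample Size Calculation unless marked as assumed.
- Pilot 6-month volume change: balance −1.06% (SD 0.53), aerobic +1.28% (SD 1.04).
- Planning values: difference 1.34, SD 1.3, α 0.05, β 0.2, stated n 16 per group.
- Assumed: m, the 6-month change without training. The documents give no value, so m is varied from 0 to −3%.

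**Step 1: what the sample size powers.** For a two-sided comparison of two means, the normal approximation is n = 2 × (1.96 + 0.84)² × (1.3/1.34)² ≈ 14.8, or 15 per group. The two-sample t-test with the noncentral t distribution gives 16, with power 0.805. The plan's 16 reproduces, and it is a sample size for the between-arm difference.

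**Step 2: identification.**
Balance effect = −1.06 − m. Aerobic effect = 1.28 − m. Difference = 1.28 − (−1.06) = 2.34, whatever m is.

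| Assumed m (%) | Balance effect (points) | Aerobic effect (points) | Difference (points) |
|---|---|---|---|
| 0 | −1.06 | +1.28 | 2.34 |
| −0.5 | −0.56 | +1.78 | 2.34 |
| −1.06 | 0.00 | +2.34 | 2.34 |
| −2 | +0.94 | +3.28 | 2.34 |
| −3 | +1.94 | +4.28 | 2.34 |

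The same balance-arm result fits harm, no effect or benefit. The aerobic effect is positive in every row, but only because every assumed m is zero or negative.

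**Step 3: how often disease course alone would look like a training effect.** Take one arm of 16, a two-sided 5% pre-post t-test and no training effect at all. The noncentrality is m/(SD/√16).
- m = −0.5, SD 1.3: −0.5/0.325 = −1.54; probability of significance 0.30.
- m = −1.0, SD 1.3: −1.0/0.325 = −3.08; probability 0.82.
- m = −0.5, SD 0.53 (the pilot balance SD): −0.5/0.1325 = −3.77; probability 0.94.

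These figures illustrate the problem on the volume scale. The documents give no corresponding inputs for connectivity, but the confounding has the same structure there.

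**Step 4: the follow-up scans.** Structural MRI is repeated 3 and 6 months after training ends. This does not provide an off-training rate, because STUDY DESIGN has participants urged, though not obliged, to keep training in that period.

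**The case against.** The strongest reply is that the plan is already comparative where it matters. Study Purpose and Rationale sets out to compare the two trainings, and Aim 1's hypothesis, the mixed model and the sample size all concern the difference between arms. The rationale says the design permits examination of mechanisms, not that it demonstrates them. It is true that a placebo-controlled design without a balance arm would have had no balance-trained participants to scan. Aim 3 is labelled exploratory. All of this stands, and it limits the point to interpretation and to the secondary analyses.

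A reader might infer more, and the documents do not support it:
- *That Aim 1 is invalid.* Its contrast is the one quantity that randomization does identify.
- *That nothing can be said about aerobic training alone.* If untrained volume is assumed never to rise, which is plausible in a degenerative disease, an increase such as +1.28% is a lower bound on benefit. That rests on the assumption, not on randomization, and it leaves the sign of the balance effect unknown.
- *That the pilot decline shows balance training to be ineffective or harmful.* Step 2 shows that it fits either of these, and benefit as well.
- *That every within-arm analysis fails.* For Aim 2's correlation of SARA change with volume change, a constant disease shift leaves Spearman's coefficient unchanged, although progression that varies between participants could affect it.

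The exploratory label does not answer the remaining point. It lowers the strength claimed for a finding but does not separate disease course from training, and the plan carries no caveat to that effect.

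**Conclusion.** The point holds in limited form. The wording in design rationale 2 and in Public Health Significance implies attribution to each training separately, which two trained arms without an untrained or natural-history comparator cannot give. The parts exposed are that wording, the before-after resting-fMRI group analysis, and the post hoc comparisons between assessments. Aim 1's hypothesis, the mixed model and the 16 per group are unaffected.

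The size depends on an untrained rate that the documents do not supply. Over an assumed 0 to −3% per 6 months, the balance effect behind the pilot mean moves by 3 points and changes sign, while the between-arm difference does not move. Superiority of aerobic over balance training would not by itself show slowing relative to no training. The conclusion assumes only that the expected change without training is unknown and may differ from zero.

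**What to change.** 1. Qualify design rationale 2 and the Public Health Significance wording: the design estimates how the two trainings differ in their effect on the cerebellum, and change within each arm is descriptive.
2. Make the between-arm difference in pre-to-post change (the arm-by-time contrast) the stated resting-fMRI group analysis. Rewording Aim 3 alone would leave the aim at odds with its analysis.
3. Confirm that arm is the tested factor in the diffusion-tensor ANCOVAs.
4. Report within-arm and between-assessment changes descriptively as change during training (training plus disease course), not as training effects or mechanisms. Label follow-up changes in the same spirit.
5. State that aerobic superiority over balance does not by itself show slowing relative to no training.

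No extra participants, visits or scans are needed. The price is a narrower claim and less power for the exploratory fMRI contrast. With equal n and SD per arm, the standard error of a difference between two mean changes is √(SD²/n + SD²/n) = √2 × SD/√n, about 1.41 times that of one arm's mean change.
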